9.3.2.2 Secondary safety outcome: case definition

Other bleeding leading to hospitalization (Annex 3, Table 7)

A patient will have to meet the following criteria to be considered a case of “other bleeding”:

- admitted to hospital with a bleeding event occurring before hospitalization (i.e. excluding in-hospital bleeding events).

Cases will be identified by hospital discharge diagnoses (ICD-9-CM).

Non-infective liver disease (Annex 3, Table 8)

A patient will have to meet both of the following criteria to be considered a case of non-infective liver disease:

- The patient having been admitted to hospital with acute liver injury.
- Free of cancer, other liver disease (including infectious hepatitis, chronic liver disease etc.), gallbladder or pancreatic disease and alcoholism.

Potential cases will be identified by hospital discharge diagnoses (ICD-9-CM) and chart review will be applied for (see [Section 9.4](#)) to define the case. If chart review is approved and laboratory values are available in the chart, the following additional criterion will be applied: an increase of more than three times the upper limit of the normal range in alanine aminotransferase (ALT) or aspartate aminotransferase (AST), or a combined increase in ALT, AST or alkaline phosphatase (AP) and total bilirubin, provided one of them is twice the upper limit of the respective normal range.

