9.3.2.3 Secondary outcomes related to effectiveness

DVT and PE (Annex 3, Table 9)

A patient will have to meet the following criteria to be considered a case of DVT or PE:

- the patient having been admitted to hospital with a diagnosis of DVT or PE
- or
- having a DVT or PE diagnosis documented in the general practitioner database.

Ischaemic stroke (Annex 3, Table 10)

A patient will have to meet the following criteria to be considered a case of ischaemic stroke: the patient having been admitted to hospital with a diagnosis of ischaemic stroke.

MI (Annex 3, Table 11)

A patient will have to meet the following criteria to be considered a case of MI: the patient having been admitted to hospital with a diagnosis of MI.

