Table 7. ICD-9-CM codes for other bleeding leading to hospitalization can be provided on request.

Table 8. ICD-9-CM codes for non-infective liver disease.

ICD-9-CM code	Description
570	Acute and subacute necrosis of liver
571.40	Chronic hepatitis, unspecified
571.41	Chronic persistent hepatitis
571.49	Chronic hepatitis, other
571.5	Cirrhosis of liver without mention of alcohol
571.6	Biliary cirrhosis
571.8	Other chronic nonalcoholic liver disease
571.9	Unspecified chronic liver disease without mention of alcohol
572.0	Abscess of liver
572.1	Portal pyemia
572.2	Hepatic coma
572.3	Portal hypertension
572.4	Hepatorenal syndrome
572.8	Other sequelae of chronic liver disease
573.0	Chronic passive congestion of liver
573.3	Hepatitis, unspecified
573.4	Hepatic infarction
573.8	Other specified disorders of liver
573.9	Unspecified disorder of liver

ICD-9-CM, International Classification of Diseases Ninth Revision, Clinical Modification.

Table 9. ICD-9-CM codes for deep vein thrombosis (DVT) and pulmonary embolism (PE)

ICD-9-CM code	Description
415.1	Pulmonary embolism and infarction
451.0	Phlebitis and thrombophlebitis of superficial leg veins
451.11	Deep vein thrombosis, femoral
451.19	Deep vein thrombosis, leg veins, spec
451.2	Thrombophlebitis, leg veins, unspec
451.81	Thrombophlebitis, iliac
451.89	Thrombophlebitis, spec
451.9	Thrombophlebitis, unspec
452.	Portal vein thrombosis
453.0	Budd-Chiari syndrome
453.1	Thrombophlebitis migrans
453.2	Thrombophlebitis of vena cava
453.3	Thrombophlebitis of renal vein
453.8	Venous embolism and thrombosis of deep vessels of lower extremity
671.30	Deep phlebothrombosis, antepartum, episode of care unspecified
671.31	Deep phlebothrombosis, antepartum, delivered, with or without mention of antepartum condition
671.32	Deep phlebothrombosis, antepartum, delivered, with mention of postpartum complication
671.33	Deep phlebothrombosis, antepartum, antepartum condition or complication
671.34	Deep phlebothrombosis, antepartum, postpartum condition or complication
671.40	Deep phlebothrombosis, postpartum, episode of care unspecified
671.41	Deep phlebothrombosis, postpartum, delivered, with or without mention of antepartum condition
671.42	Deep phlebothrombosis, postpartum, delivered, with mention of postpartum complication
671.43	Deep phlebothrombosis, postpartum, antepartum condition or complication
673.20	Obstetrical blood-clot embolism, unspecified as to episode of care or not applicable

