673.21	Obstetrical blood-clot embolism, delivered, with or without mention of antepartum condition
673.22	Obstetrical blood-clot embolism, delivered, with mention of postpartum complication
673.23	Obstetrical blood-clot embolism, antepartum condition or complication
673.24	Obstetrical blood-clot embolism, postpartum condition or complication

ICD-9-CM, International Classification of Diseases Ninth Revision, Clinical Modification.

Table 10. ICD-9-CM codes for ischaemic stroke

ICD-9-CM code	Description
433.0	Occlusion and stenosis of basilar artery
433.1	Occlusion and stenosis of carotid artery
433.2	Occlusion and stenosis of vertebral artery
433.3	Occlusion and stenosis of precerebral arteries mult/bilat
433.8	Occlusion and stenosis of precerebral arteries, spec
433.9	Occlusion and stenosis of precerebral arteries, unspec
434.0	Cerebral thrombosis
434.1	Cerebral embolism
434.9	Occlusion of cerebral artery, unspec
435.0	Basilar artery syndrome
435.1	Vertebral artery syndrome
435.2	Subclavian steal syndrome
435.8	Transient ischemic attack, spec.
435.9	Transient ischemic attack, unspec.
436	Acute but ill-defined cerebrovascular disease

ICD-9-CM, International Classification of Diseases Ninth Revision, Clinical Modification.

Table 11. ICD-9-CM codes for myocardial infarction (MI)

ICD-9-CM code	Description
410.0	MI, acute, anterolateral
410.1	MI, acute, anterior, NOS
410.2	MI, acute, inferolateral
410.3	MI, acute, inferoposterior
410.4	MI, acute, other inferior wall, NOS
410.5	MI, acute, other lateral wall
410.6	MI, acute, true posterior
410.7	MI, acute, subendocardial
410.8	MI, acute, spec.
410.9	MI, acute, unspec.

ICD-9-CM, International Classification of Diseases Ninth Revision, Clinical Modification.

Table 12 ICD-9-CM codes related to renal impairment

ICD-9-CM code	Description
250.4	Diabetes with renal manifestations
249.4	Secondary diabetes mellitus with renal manifestations
403	Hypertensive chronic kidney disease
404	Hypertensive heart and chronic kidney disease
581	Nephrotic syndrome
583.81	Nephritis and nephropathy, NOS, in diseases classified elsewhere
585	Chronic kidney disease (no subcodes available)
586	Renal failure, unspecified
593.6	Postural proteinuria
791.0	Proteinuria
V42.0	Kidney transplant
V45.1	Renal dialysis status
V56	Encounter for dialysis and dialysis catheter care

ICD-9-CM, International Classification of Diseases Ninth Revision, Clinical Modification.

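### Table 8 lists chronic liver disease among the liver outcome codes although Section 9.3.2.2 excludes it, and no code-only rule is given if chart review is refused

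*Protocol*

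**What the plan says.** **Liver.** Protocol Section 9.3.2.2 requires two criteria to be met together. The first concerns the reason for admission: "The patient having been admitted to hospital with acute liver injury". The second sets out which other conditions rule a patient out as a case: "Free of cancer, other liver disease (including infectious hepatitis, chronic liver disease etc.), gallbladder or pancreatic disease and alcoholism".

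On case finding it says: "Potential cases will be identified by hospital discharge diagnoses (ICD-9-CM) and chart review will be applied for". A laboratory threshold is added on a condition: "If chart review is approved and laboratory values are available in the chart, the following additional criterion will be applied". Section 9.4 states that chart review requires approval from the Dutch National Medical Register and from the individual hospitals. Annex 3, Table 8 gives 19 ICD-9-CM codes for this outcome, among them 571.5, "Cirrhosis of liver without mention of alcohol".

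**Ischaemic stroke.** Section 9.3.2.3 defines a case as "the patient having been admitted to hospital with a diagnosis of ischaemic stroke" and refers to Table 10, whose entries include 435.9, "Transient ischemic attack, unspec".

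**DVT/PE.** Section 9.3.2.3 accepts a hospital or GP diagnosis of DVT or PE and refers to Table 9, whose entries include 451.0, "Phlebitis and thrombophlebitis of superficial leg veins".

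**Analysis.** Section 9.7.2 plans crude incidence rates in both cohorts for every outcome, counting the first admission for that outcome during follow-up. Adjusted rate ratios are planned for three adverse outcomes, which the Abstract identifies as the primary ones.

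**The concern.** A patient correctly coded with cirrhosis or chronic hepatitis fails the second liver criterion, so those codes describe people who should be removed from the case series. If chart review goes ahead, they add work but few or no valid cases. If it is refused, fully or at some hospitals, Table 8 is the only case-finding tool the protocol leaves. Admissions for long-standing liver disease could then be counted as liver events after the start of treatment.

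At stake is the meaning of a secondary safety outcome. Wrongly counted cases raise the crude rate in both cohorts. If the cohorts are then compared and the extra cases are unrelated to treatment, a real difference would look smaller than it is, which for a safety outcome is falsely reassuring.

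A lesser concern of the same kind applies to stroke and DVT/PE, where the code lists reach beyond the conditions the outcomes are named after.

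**Working it through.** The protocol states no figure for this point, so there is nothing to reproduce. The check sets each definition against its code list, counting by printed label.

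**Table 8 against Section 9.3.2.2**

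- Total: 19 codes.
- Label contains the word chronic: 571.40, 571.41, 571.49, 571.8, 571.9, 572.8, 573.0 = 7.
- Cirrhosis: 571.5, 571.6 = 2.
- Chronic or cirrhosis: 7 + 2 = 9, and 9/19 = 47%.
- Liver abscess and portal pyemia (572.0, 572.1) = 2. Their labels do not say infective, but they sit poorly in an outcome called non-infective.
- Remaining: 19 − 9 − 2 = 8, namely 570, 572.2, 572.3, 572.4, 573.3, 573.4, 573.8, 573.9. Only 570 is labelled acute.

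**What happens without chart review.** Section 9.3.2.2 gives chart review the task of defining the case, and Section 9.4 makes it subject to outside approval. Neither section says how the two criteria are to be applied from codes alone. Section 9.7.2 counts the first qualifying admission in follow-up, and no code-based removal of patients with liver disease before the index date is stated.

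**Possible size, under assumption.** Let p be the share of code-flagged cases in the comparator cohort that are true cases. The protocol does not give p, so a range is shown.

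- Overstatement of the comparator crude rate = 1/p.
- If false positives occur at the same rate in both cohorts, observed rate ratio = p × RR + (1 − p).

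For an illustrative true rate ratio of 1.50:

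- p = 0.9: rate × 1.11; ratio 0.9 × 1.5 + 0.1 = 1.45
- p = 0.7: rate × 1.43; ratio 0.7 × 1.5 + 0.3 = 1.35
- p = 0.5: rate × 2.00; ratio 0.5 × 1.5 + 0.5 = 1.25
- p = 0.3: rate × 3.33; ratio 0.3 × 1.5 + 0.7 = 1.15

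**Table 10 (15 codes).** Cerebral thrombosis, embolism or occlusion (434.x): 3. Precerebral occlusion and stenosis (433.x): 6. 435.x: 5, of which 2 are labelled TIA. Ill-defined cerebrovascular disease (436): 1. Section 7 names stroke and TIA as separate risk factors in the atrial fibrillation indication, so the protocol itself distinguishes them.

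**Table 9 (28 codes).** DVT, PE, deep phlebothrombosis or obstetric clot embolism by label: 4 + 9 + 5 = 18, and 18/28 = 64%. The other 10 are superficial, unspecified or other-site entries, including 451.0 and the portal, hepatic and renal vein codes (452, 453.0, 453.3).

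**The case against.** The best defence is that Table 8 is a screening list. The text calls its output potential cases, requires both criteria and assigns the decision to chart review; Section 9.8 allows an application for review for any outcome where more information is needed. A deliberately wide net before confirmation is legitimate. This stands as long as review takes place. It does not explain why codes that name an excluded condition are listed as outcome codes, and it gives no help where approval is withheld. An analysis plan could add a fallback, but the protocol itself prints both the definition and the list that conflicts with it.

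Several further objections stand and limit the point:

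- A reader might infer that all three lists capture conditions their definitions exclude. That is true of liver only. Section 9.3.2.3 states no exclusion for stroke or DVT/PE, so those lists are broad rather than contradictory.
- A reader might infer from the counts that these outcomes mostly measure something else. Code counts are not case counts, and the protocol gives neither case mix nor positive predictive value. In Table 9 most codes fit the outcome.
- A reader might assume that the 433.x codes bring in elective carotid admissions. The labels do not require an infarction, but the documents do not say which admissions are coded there.
- Bias toward 1 is not assured. TIA and thrombosis at other sites may respond to anticoagulation, and in a non-randomised comparison the extra events may differ between cohorts for other reasons.
- No adjusted rate ratio is specified for these outcomes, and the liver objective in Section 8.2 does not mention a comparison. The firmer harm is to the crude rates.

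**Conclusion.** The liver point holds. Table 8 and Section 9.3.2.2 contradict each other on 9 of 19 codes, and 2 more fit badly with the outcome's name. If the plan were followed without chart review, excluded conditions would be counted as cases and crude liver incidence would be too high. The amount cannot be derived from the protocol: the 1.1-fold to 3.3-fold range rests wholly on assumed true-case shares of 90% to 30%. Dilution of a between-cohort comparison requires two further assumptions: that such a comparison is made, and that the extra cases are unrelated to treatment.

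For ischaemic stroke and DVT/PE the supportable statement is weaker: Tables 10 and 9 are wider than the outcome names, and the results need labelling to match.

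All three are secondary outcomes. The primary comparison of intracranial, gastrointestinal and urogenital bleeding is unaffected.

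**What to change.** **Liver (needed).** In Annex 3, move 571.40, 571.41, 571.49, 571.5, 571.6, 571.8, 571.9, 572.8, 573.0, 572.0 and 572.1 from Table 8 to an exclusion list. State in Section 9.3.2.2 that, where chart review is not available, a case is an admission with one of the remaining codes compatible with acute injury, for example 570, 573.3, 573.4, 573.8 and 573.9, in a patient with no code on the exclusion list. The placement of 572.2, 572.3 and 572.4, whose labels settle nothing either way, needs a clinical decision; they could be kept for a sensitivity analysis. Report how many cases were confirmed by chart and how many by code alone. Make the change before the lists are extended to ICD-10, as Section 9.4 foresees, so that the conflict is not carried over.

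**Stroke and DVT/PE (advisable).** Report TIA and superficial phlebitis separately, or rename the outcomes to match the lists. Add a narrow-code sensitivity analysis that leaves out 433.x and 435.x for stroke, and 451.0 with the portal, hepatic and renal vein codes for DVT/PE.

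**Cost.** An Annex edit and a few lines of text. Fewer events will be counted and intervals will widen. Some true strokes may be coded 433.x and would be lost under the narrow definition, so it is proposed as a sensitivity analysis and not as a replacement.
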